### **Ventricular septal perforation**

Angiographic or echocardiographic evidence of a new septal perforation during or after the TAVI procedure.

## **CARDIAC TAMPONADE**

Clinical syndrome caused by the accumulation of fluid in the pericardial space, resulting in reduced ventricular filling and subsequent hemodynamic compromise.

## **CARDIOGENIC SHOCK**

Patient was, at the time of procedure, in a clinical state of hypoperfusion sustained for greater than 30 minutes, according to either of the following criteria:

1. Systolic BP < 80 and/or Cardiac Index < 1.8 despite maximal treatment; or
2. IV inotropes and/or IABP necessary to maintain Systolic BP > 80 and/or CI > 1.8

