#### C.3.6.2 Exclusion Criteria

Subjects are NOT eligible for trial participation if they meet ANY of the following exclusion criteria:

1. Subject has refused surgical aortic valve replacement (SAVR) as a treatment option;
2. Any condition considered a contraindication for placement of a bioprosthetic valve (i.e. subject requires a mechanical valve);

3. A known hypersensitivity or contraindication to all anticoagulation/antiplatelet regimens (or inability to be anticoagulated for the index procedure), nitinol, or sensitivity to contrast media which cannot be adequately pre-medicated;
4. Blood dyscrasias as defined: leukopenia (WBC <1000mm^3), thrombocytopenia (platelet count <50,000 cells/mm^3), history of bleeding diathesis or coagulopathy;
5. Ongoing sepsis, including active endocarditis;
6. Any condition considered a contraindication to extracorporeal assistance;
7. Any percutaneous coronary or peripheral interventional procedure performed within 30 days prior to randomization (Subjects with recent placement of drug eluting stent(s) should be assessed for ability to safely proceed with SAVR within the protocol timeframe);
8. Symptomatic carotid or vertebral artery disease or successful treatment of carotid stenosis within six weeks of randomization;
9. Cardiogenic shock manifested by low cardiac output, vasopressor dependence, or mechanical hemodynamic support;
10. Recent (within 6 months of randomization) cerebrovascular accident (CVA) or transient ischemic attack (TIA);
11. Active gastrointestinal (GI) bleeding that would preclude anticoagulation;
12. Subject refuses a blood transfusion;
13. Severe dementia (resulting in either inability to provide informed consent for the trial/procedure, prevents independent lifestyle outside of a chronic care facility, or will fundamentally complicate rehabilitation from the procedure or compliance with follow-up visits);
14. Multivessel coronary artery disease with a Syntax score >22 and/or unprotected left main coronary artery (Syntax score calculation is not required for patients with history of previous revascularization if repeat revascularization is not planned);
15. Estimated life expectancy of less than 24 months due to associated non-cardiac co-morbid conditions;
16. Other medical, social, or psychological conditions that in the opinion of the Investigator precludes the subject from appropriate consent or adherence to the protocol required follow-up exams;

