### C.6.8 Secondary Endpoints

#### C.6.8.1 Secondary Endpoints Compared Between TAVI and SAVR

1. Incidence of Major Adverse Cardiovascular and Cerebrovascular Events (MACCE) at 30 days, 6 months, 12 months, 18 months, 24 months, and annually thereafter up to 5 years. MACCE is defined as a composite of:

- All-cause death
- Myocardial infarction (MI)
- All stroke, and
- Reintervention (defined as any cardiac surgery or percutaneous reintervention catheter procedure that repairs, otherwise alters or adjusts, or replaces a previously implanted valve)

MACCE-incidence estimates will be provided for the two treatment groups at 30 days, 6 months, 12 months, 18 months, 24 months, and annually thereafter up to 5 years. The statistical method will be the Bayesian version of a comparison of proportions (with predictions).

Additionally, incidence of MACCE will be compared at 30 days or hospital discharge, whichever is later. The statistical method will be the Bayesian version of a comparison of proportions.

2. The occurrence of individual MACCE components at 30 days, 6 months, 12 months, 18 months, 24 months, and annually thereafter up to 5 years.

MACCE components will be summarized and their incidence estimates provided at 30 days, 6 months, 12 months, 18 months, 24 months, and annually thereafter up to 5 years. The statistical method will be the Bayesian version of a comparison of proportions (with predictions).

3. Major Adverse Events (MAE) and individual components at 30 days, 6 months, 12 months, 18 months, 24 months, and annually thereafter up to 5 years.

MAE events and individual components will be summarized and the incidence of MAEs will be provided at 30 days, 6 months, 12 months, 18 months, 24 months, and annually thereafter up to 5 years. The statistical method will be the Bayesian version of a comparison of proportions (with predictions).

Additionally, incidence of major vascular complications and incidence of major or life-threatening bleeding events at 30 days or hospital discharge, whichever is longer, will also be compared using the Bayesian version of a comparison of proportions.

4. Incidence of Early safety at 30 days defined as a composite of:

- All-cause mortality
- All stroke (disabling and non-disabling)
- Life-threatening bleeding
- Acute kidney injury—Stage 2 or 3 (including renal replacement therapy)
- Coronary artery obstruction requiring intervention
- Major vascular complication

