### C.6.11 Heterogeneity/Poolability

A poolability analysis among investigational centers, access site (ilio-femoral or non-ilio-femoral), need for revascularization, and primary baseline demographics will be performed for the primary endpoint and will be described in the SAP. In particular, the primary endpoint and key secondary endpoints such as MACCE and MAE incidence will be examined for differences in outcome between genders, need for revascularization, and between access routes. Additionally, tests for these outcomes will be performed to evaluate potential interactions between treatment and gender and between treatments and need for revascularization and between treatment and access site.

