#### **MAJOR ADVERSE EVENT (MAE)**

Major Adverse events include the following:

- MACCE
- Acute kidney Injury
- Cardiac tamponade
- Prosthetic valve dysfunction
- Cardiogenic shock
- Prosthetic valve endocarditis
- Life-threatening, disabling or major bleeding
- Major vascular complication
- Cardiac Perforation
- Valve malpositioning

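### The definition of cardiogenic shock, a component of the MAE composite, covers shock at the time of the procedure but not shock that begins afterwards

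*Combined protocol and SAP*

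**What the plan says.** The Cardiogenic Shock entry in O.2 reads "Patient was, at the time of procedure, in a clinical state of hypoperfusion sustained for greater than 30 minutes" and then requires either of two criteria. The first is a systolic pressure below 80 and/or a cardiac index below 1.8 despite maximal treatment. The second is "IV inotropes and/or IABP necessary to maintain Systolic BP > 80 and/or CI > 1.8". Neither criterion mentions timing.

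The MAE entry in O.2 ("Major Adverse events include the following") lists "Cardiogenic shock" as a component, as does C.5.1.4. Neither list gives shock a definition of its own.

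Secondary endpoint 3 in C.6.8.1 is "Major Adverse Events (MAE) and individual components at 30 days" and at 6, 12, 18 and 24 months, then yearly to 5 years. Its analysis text adds that "MAE events and individual components will be summarized and the incidence of MAEs will be provided at 30 days" and at the later times. Endpoint 17 counts index-procedure-related MAEs up to the end of the 30-day visit. C.6.11 places MAE among the "key secondary endpoints such as MACCE and MAE incidence will be examined" for differences by gender, need for revascularization and access route.

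The only other descriptive wording for shock is exclusion criterion 9 in C.3.6.2: "Cardiogenic shock manifested by low cardiac output, vasopressor dependence, or mechanical hemodynamic support". It serves eligibility only.

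**The concern.** The past tense and the anchor to the procedure describe a patient's condition going into or during the intervention. An outcome definition has to capture what happens afterwards as well. If the words are applied as they stand, a patient who goes into shock on the ward or at month 6 does not have the MAE component called cardiogenic shock, however clearly the haemodynamic criteria are met.

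At stake is the comparison of a serious complication between TAVI and surgery, both as a separate component and within a composite that C.6.7.2 assigns to inferential analysis in the ITT and mITT populations. Because treatment is not blinded (C.4.5), a definition that each reader must stretch also leaves room for inconsistent classification.

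**Working it through.** No arithmetic applies. The check sets the timing wording side by side and then runs typical cases through it.

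**Timing in comparable O.2 entries**

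| Entry | Timing as worded |
|---|---|
| Cardiogenic shock | A state at the time of the procedure |
| Cardiac tamponade (the preceding entry) | No time limit |
| Ventricular septal perforation; mitral apparatus damage | During or after the TAVI procedure |
| Coronary obstruction | During or after the TAVI procedure |
| Valve embolization | During or after deployment |
| Myocardial infarction | Separate definitions up to 72 hours and beyond 72 hours |
| Acute kidney injury | Up to 7 days after the index procedure |

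Shock is the only one of these whose wording stops at the procedure.

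**Cases under the literal wording** (each meets the 30-minute duration and one haemodynamic criterion)

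| Case | Shock component | MAE composite |
|---|---|---|
| Onset during the procedure | Counted | Counted |
| Onset between randomization and procedure, still present at the procedure | Can be counted | Can be counted |
| Onset day 3, fatal | Missed | Counted, through all-cause death in MACCE |
| Onset day 3, survived, with acute kidney injury or another MAE | Missed | Counted, through the other event |
| Onset day 3, survived, no other MAE | Missed | Missed |
| Onset month 6, survived, no other MAE | Missed | Missed |

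Three consequences follow.

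1. The component can gain no event after the procedure. The number of subjects with shock at 30 days is the same as the number at 5 years.
2. For endpoint 17, shock on day 3 that results directly from the index procedure fits the O.2 entry for procedure-related events but not the shock entry, so it is not counted as a shock MAE.
3. The composite loses only subjects in the last two rows.

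**Is the gap closed elsewhere?** C.5.2.6 and Section D list shock as an anticipated event without defining it. C.5.3 ties adjudication to the protocol's definitions and the CEC charter. The charter is not among the documents, so any operating rule in it cannot be seen. Nothing in the text available extends the definition past the procedure.

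**The case against.** Several points on the other side are sound.

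- **A time-limited component is not an error in itself.** Acute kidney injury is also an MAE component and is limited to 7 days. It is simply carried forward in later reports. This stands: the long reporting schedule alone does not prove a mistake. The difference is that the kidney-injury window runs past the procedure and is stated as an outcome window, whereas the shock wording is neither.
- **Little inference depends on it.** The primary endpoint is all-cause mortality or disabling stroke. The labeling hierarchy in C.6.10 takes only major vascular complications and major or life-threatening bleeding from objective 3. Endpoint 17 is descriptive. This stands.
- **Safety information is not lost.** Under C.5.2, new or worsening events are recorded through 24 months, and serious and cardiovascular events after that. The DSMB reviews serious events. This stands, but recording an event does not make it meet the component's definition.
- **The composite has many other routes in.** Death, infarction, stroke, reintervention, kidney injury, tamponade, perforation and major bleeding will pick up some of these patients. This stands and limits the loss, though it does nothing for the component.

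A reader might infer something stronger: that the component is empty by construction, because exclusion 9 bars patients in shock, and so will read near 0% in both arms. The documents do not support that. Shock arising during TAVI or surgery fits the words and cannot be screened out. Eligibility is confirmed before randomization and the procedure may follow up to 30 days later (C.4.5), so shock arising in between can also qualify.

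**Conclusion.** The concern holds for shock with onset after the procedure. As worded, the component misses all of it, and the composite misses the part that is non-fatal and unaccompanied by another MAE. The effect is confined to secondary endpoints 3 and 17 and to analyses built on MAE incidence, such as those in C.6.11. The primary endpoint and the labeling claims are untouched.

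The size of the loss cannot be estimated. The documents give no rate of post-procedural shock in either arm and no proportion of such patients who would have another MAE. A bias in favour of one arm might also be inferred, but the documents do not show one, since nothing in them says how post-procedural shock would divide between TAVI and surgery.

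The conclusion assumes that the definition is applied literally and that the CEC charter does not already widen it. The correction is cheap and should be made.

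**What to change.** Split the O.2 entry in two. Keep the present sentence for baseline status only. Add an outcome definition: new-onset hypoperfusion that meets the existing duration and either existing criterion, with onset during or after the index procedure. Several neighbouring entries already use this form, but three of them refer to the TAVI procedure only, so the new text should name the index procedure and thereby cover both arms. Point the MAE lists in C.5.1.4 and O.2 to the outcome definition.

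Align the CEC charter, and re-adjudicate shock already recorded as an adverse or serious adverse event where source data allow.

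The cost is a short amendment and some re-adjudication. Some late events may lack the blood pressure, cardiac index or duration needed to classify them. Those should be reported as unclassifiable, by arm, and not silently counted as no event.

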## **CHRONIC RENAL INSUFFICIENCY**

Kidney damage or glomerular filtration rate (GFR) <60 mL/min/1.73 m^2 for or ≥3 months. Kidney damage is defined as pathologic abnormalities or markers of damage, including abnormalities in blood or urine test or imaging studies.

## **CONDUCTION DISTURBANCE REQUIRING PERMANENT PACEMAKER IMPLANTATION**

ACC/AHA 2006 Guidelines for the Management of Patients with Valvular Heart Disease (published in the August 1, 2006, issues of Journal of the American College of Cardiology and Circulation)

Any disturbance in the cardiac electrical conduction system that meets the American College of Cardiology (ACC)/American Heart Association (AHA)/ Heart Rhythm Society (HRS) Class I or IIa Guidelines for Device-Based Therapy of Cardiac Rhythm Abnormalities for Acquired Atrioventricular Block in Adults or Permanent Pacing in Chronic Bifascicular Block.

## **CONVERSION TO OPEN HEART SURGERY**

Valve Academic Research Consortium (VARC)-2; Updated Standardized Endpoint Definitions for Transcatheter Aortic Valve Implantation (TAVI); 2012-10-09.

Conversion to open sternotomy during the TAVI procedure secondary to any procedure-related complications.

## **CORONARY OBSTRUCTION**

Valve Academic Research Consortium (VARC)-2; Updated Standardized Endpoint Definitions for Transcatheter Aortic Valve Implantation (TAVI); 2012-10-09.

Angiographic or echocardiographic evidence of a new, partial or complete, obstruction of a coronary ostium, either by the valve prosthesis itself, the native leaflets, calcifications, or dissection, occurring during or after the TAVI procedure.

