**Table 3: Schedule of Assessments**

Parameter	Screening	RANDOMIZATION	Baseline	Procedure	Discharge	30 days	3 Months	6 Months	12 Months	18 Months	24 Months	3 – 5 years
			(within 14 days of procedure)									
Informed consent (and in US HIPAA Authorization)	•											
Inclusion/Exclusion	•			•*								
Demographics and Medical history	•											
Physical Examination	•		•		•	•		•	•	•	•	•
Clinical Assessments	•											
NYHA Class	•		•			•		•	•	•	•	•
Risk Assessments: STS Risk Score, Logistic EuroSCORE, EuroSCORE II, SYNTAX Score, and Katz Index	•											
Co-morbidities	•											
Concomitant Medications 			•	•	•	•		•	•	•	•	
Routine Laboratory Tests	•		•	• 	•	• 						
Neurological Assessments  (NIHSS, mRS, MMSE-2:SV and Additional Neurological Assessments) 			•		•				•		•	
Abbreviated Neurological Assessment (NIHSS only)				• 		•		•		•		•
Transthoracic Echocardiogram (TTE)	•			• 				•	•		•	•
Computed Tomography (CT) Angiogram (MSCT required at screening) 	•											
Coronary Arteriogram	•			(•)								
Aortogram				(•)								
12-lead Electrocardiogram	•		•	• 	•	•		•	•	•	•	•
6 Minute Walk Test			•			•			•		•	
Quality of Life Questionnaires (EQ-5D, KCCQ, and SF-36)			• 			•	• 	•	•	•	•	•
Adverse Events			•	•	•	•		•	•	•	•	• 

- \* Document any changes to subject condition that affect inclusion/exclusion criteria, confirm the subject does not meet any exclusion criteria specific to the Index Procedure (eg. percutaneous coronary or peripheral intervention and evidence of an acute myocardial infarction which must not occur within 30 days prior to the index procedure)
- (•) TAVI subjects only (SAVR subjects will not have these assessments)
  -  Laboratory test results must be performed pre-procedure and CK to be obtained within 8-12 hours post-procedure
  -  Pre-procedure
  -  Only hemoglobin, creatinine and creatinine clearance are required to be collected
  -  Electrocardiogram within 48 hours post-procedure
  -  TTE to be completed at least 24hours post-procedure but prior to discharge (and no later than 7 days post procedure) to assess device success

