#### *C.5.3 Clinical Events Committee (CEC)*

An independent Clinical Events Committee (CEC) will review and adjudicate, at a minimum, all deaths and primary endpoint related adverse events. The CEC will consist of, at a minimum, interventional cardiologists and cardiac surgeons who are not participants in the trial. Additional specialist, such as neurologists, may also be selected as part of the CEC.

The purpose of the CEC is to conduct a medical review and classify/adjudicate, at a minimum, all deaths and/or clinical endpoints collected in the trial according to definitions and processes outlined in the Medtronic CoreValve™ SURTAVI Trial protocol and the CEC charter, which will be developed and approved by Medtronic and the CEC members.

All applicable events will be reviewed and adjudicated by a minimum of two CEC members. All other events will be reviewed and adjudicated by qualified internal Medtronic safety individual(s) to ensure they should not be adjudicated by the full CEC and that the events are appropriately classified by the investigator.

Prior to event adjudication, the CEC will draft a charter to establish explicit rules outlining the minimum amount of data required and the algorithm followed in order to classify/adjudicate a trial endpoint related clinical event. CEC decisions will be documented in meeting minutes, which will be maintained in the trial file.

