- Valve-related dysfunction requiring repeat procedure (BAV, TAVI, or SAVR)
- All-cause death

Early safety composite endpoint-incidence estimates will be provided for the two treatment groups at 30 days. The statistical method will be the Bayesian version of a comparison of proportions.

5. Incidence of Clinical Efficacy (after 30 days) at 6 months, 12 months, 18 months, 24 months and annually thereafter up to 5 years. Clinical efficacy defined as a composite of:
- All-cause mortality
  - All stroke (disabling and non-disabling)
  - Requiring hospitalizations for valve-related symptoms or worsening congestive heart failure
  - NYHA class III or IV
  - Valve-related dysfunction (mean aortic valve gradient  $\geq 20$  mmHg, EOA  $\leq 0.9$ - $1.1$   $\text{cm}^2$  and/or DVI  $< 0.35$  m/s, AND/OR moderate or severe prosthetic valve regurgitation\*)

Clinical efficacy estimates will be provided for the two treatment groups at 6 months, 12 months, 18 months, 24 months and annually thereafter up to 5 years. The statistical method will be the Bayesian version of a comparison of proportions (with predictions).

\*Refers to VARC-2 definitions

6. Incidence of Time-Related Safety at 30 days, 6 months, 12 months, 18 months, 24 months and annually thereafter up to 5 years. Time-Related Safety defined as a composite of:
- Structural valve deterioration:
    - Valve-related dysfunction (mean aortic valve gradient  $\geq 20$  mmHg, EOA  $\leq 0.9$ - $1.1$   $\text{cm}^2$  and/or DVI  $< 0.35$  m/s, AND/OR moderate or severe prosthetic valve regurgitation\*)
    - Requiring repeat procedure (TAVI or SAVR)
  - Prosthetic valve endocarditis
  - Prosthetic valve thrombosis
  - Thromboembolic events (eg. stroke)
  - VARC bleeding, unless clearly unrelated to valve therapy (eg. trauma)

Time related safety composite endpoint-incidence estimates will be provided for the two treatment groups at 30 days, 6 months, 12 months, 18 months, 24 months and annually thereafter up to 5 years. The statistical method will be the Bayesian version of a comparison of proportions (with predictions).

\*Refers to VARC-2 definitions

7. Conduction disturbance requiring permanent pacemaker implantation at 30 days, 6 months, 12 months, 18 months, 24 months, and annually thereafter up to 5 years.

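### As worded, the definition of coronary obstruction covers only the TAVI procedure, yet the event is a component of Early Safety, which is compared between TAVI and SAVR

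*Combined protocol and SAP*

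**What the plan says.** Protocol section O.2, Coronary Obstruction, cites VARC-2 and asks for angiographic or echocardiographic evidence of a new partial or complete obstruction of a coronary ostium. It lists the possible causes and closes with "calcifications, or dissection, occurring during or after the TAVI procedure". It mentions neither surgery nor the index procedure, and no other definition of the term appears in the text reviewed.

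Section C.6.8.1, headed "Secondary Endpoints Compared Between TAVI and SAVR", has Early Safety at 30 days as item 4. One of its components is "Coronary artery obstruction requiring intervention"; the synopsis lists the same component. On the analysis, the section states: "Early safety composite endpoint-incidence estimates will be provided for the two treatment groups at 30 days", and then: "The statistical method will be the Bayesian version of a comparison of proportions".

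Section C.5.3 has the CEC classify events "according to definitions and processes outlined in the Medtronic CoreValve™ SURTAVI Trial protocol and the CEC charter". Section C.4.5 does not allow a subject randomized to SAVR to cross over to TAVI.

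**The concern.** A composite compared between randomized arms needs each component to be definable in both. Here the surgical arm has no procedure that satisfies the closing condition of the definition. Suppose a surgical prosthesis or displaced calcium blocks a coronary ostium, and the subject needs a coronary intervention and recovers without any other listed event. Read literally, that subject is free of Early Safety events, while a TAVI subject with the same course is not.

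Two things would be at stake: a SAVR composite rate that is too low, and a component table whose surgical entry reflects wording as well as outcome. Both run against TAVI.

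**Working it through.** **Text check.**

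1. Scope of the term. The O.2 definition is tied to the TAVI procedure.
2. Use of the term. C.6.8.1 item 4 applies it to both arms and compares them.
3. House style. Where O.2 intends both arms, it uses neutral wording: acute kidney injury is timed from the index procedure, and so is peri-procedural myocardial infarction. TAVI-only wording is therefore not a convention for either procedure. Conversion to open heart surgery and unplanned cardiopulmonary bypass are also TAVI-worded, but they describe TAVI-specific events and are not Early Safety components.
4. Other routes into the composite. Death, any stroke, life-threatening bleeding, stage 2 or 3 kidney injury, major vascular complication, and valve dysfunction needing a repeat procedure would each still count a SAVR subject. O.2 counts any aortic dissection as a major vascular complication, so much of the dissection mechanism is already covered. Myocardial infarction is not an Early Safety component, so it does not fill the gap.
5. Supplementary analysis. The list of terms in C.6.12.2 to be re-analysed under VARC-I omits coronary obstruction.

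The gap is therefore a SAVR subject with ostial obstruction needing intervention and no other listed event.

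**Size (illustration only).** The plan gives no figure to reproduce: it has no Early Safety rate, margin or power. The one documented input is the mITT sample of 1600 at 1:1 (C.6.5.2), so about 800 per arm. The surgical rate of the event (0.2% to 1%) and the composite rate are assumptions.

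- Subjects affected, before overlap: 0.002 × 800 = 1.6 and 0.01 × 800 = 8, so about 2 to 8.
- Standard error of the difference with an assumed 15% in each arm: √(2 × 0.15 × 0.85 / 800) = 0.0179.
- Shift in standard errors: 0.002 / 0.0179 = 0.11 and 0.01 / 0.0179 = 0.56.

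A second illustration takes equal true composite rates p and lets a fraction u of SAVR subjects go uncounted for want of any other component event. Then SE = √[p(1−p)/800 + (p−u)(1−p+u)/800]. The chance of a one-sided 0.025 result favouring SAVR is 1 − Φ(1.96 − u/SE), against 2.5% when u = 0.

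| u | Uncounted of 800 | p = 10% | p = 20% |
|---|---|---|---|
| 0.25% | 2 | 3.7% | 3.3% |
| 0.5% | 4 | 5.2% | 4.4% |
| 1% | 8 | 10.1% | 7.3% |

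In this table u is already net of overlap. The gross surgical rate would have to be higher than u to produce each row.

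**The case against.** The strongest reply is that the text does not show the component to be unscorable in the surgical arm. The CEC works from its charter as well as from the protocol. C.5.3 says the charter will set explicit classification rules, and neither the charter nor the separate SAP is in the text reviewed. The composite names coronary artery obstruction without a cross-reference to O.2, and the TAVI wording looks imported from a TAVI consensus document. All of this stands as a limit. A reader might infer that the SAVR rate is fixed at zero by definition; the documents do not establish that. They show only that the protocol's own definition does not reach SAVR and that nothing in the text reviewed extends it.

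A reader might also infer a detection bias, because Table 3 marks the procedural coronary arteriogram and aortogram "TAVI subjects only (SAVR subjects will not have these assessments"). That is weak. The component counts only obstruction needing intervention, and the definition accepts echocardiographic evidence. Both arms have CK at 8 to 12 hours and whenever ischemia is suspected, an ECG within 48 hours, and a transthoracic echocardiogram before discharge (C.4.7.1, C.4.7.2, C.4.8). For SAVR, transesophageal echocardiography before the end of surgery is recommended, with attention to new wall-motion abnormalities.

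Finally, Early Safety carries little inferential weight. It is not among the 18 tests in C.6.10.1, and C.6.10 says that secondary objectives outside that hierarchy will not support labeling claims. C.6.7.2 does not list it among the endpoints for inferential statistics, although C.6.8.1 names a comparison method. This limits the consequence but does not remove the mismatch.

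**Conclusion.** The definition and its use do not match and should be reconciled. Followed literally, and absent a charter rule to the contrary, the protocol leaves out SAVR subjects whose only Early Safety event is a coronary ostial obstruction needing intervention. The SAVR rate is then too low and the comparison is biased against TAVI.

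The effect is small and its size is not known from the documents. The figure of 2 to 8 of 800, or about 0.1 to 0.6 standard errors, is an upper figure. It rests on an assumed surgical rate of 0.2% to 1% and, for the standard errors, an assumed 15% composite rate, with no deduction for subjects who qualify through another component.

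It would be wrong to infer that the primary result, type I error control or any labeling claim is affected. The issue is confined to one non-primary, non-labeling comparison and its component table, and its direction cannot produce a false claim in favour of TAVI.

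**What to change.** In O.2, end the coronary obstruction definition with a reference to events during or after the index procedure, whether TAVI or SAVR, in line with the acute kidney injury and peri-procedural infarction entries. Put the same rule in the CEC charter and state there that it governs the Early Safety component in both arms. Then have the CEC adjudicate under that definition any SAVR coronary events already collected as adverse events. If the charter already extends the term, it is enough to say so in O.2.

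The cost is one phrase in the protocol, a matching line in the charter, and committee time for what should be a small number of events. No new data collection is needed, because C.5.2 already captures all new or worsening adverse events through the 24-month visit. Sample size and the testing hierarchy do not change.
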